15.3. Exposure and Compliance

The extent of exposure to study drug in each treatment group will be summarized by total number of days of exposure, total number of applications, number of missed applications and number and percentage of subjects who are compliant. A subject will be considered compliant with the dosing regimen if the subject applied 80% to 120% of the expected number of applications while enrolled in the study.

15.4. Efficacy Measures

15.4.1. Primary Efficacy Analysis

The primary efficacy analysis will be conducted with an analysis of variance (ANOVA) model with the percentage change from Baseline to Week 8 in EASI score as the dependent variable and treatment group and the randomization stratification variable as factors. The two arms will be compared using a one-sided test at the alpha=0.05 level of significance.

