The primary efficacy analysis will be conducted in the intent-to-treat population (all randomized subject) using an analysis of variance (ANOVA) model with the percentage change from Baseline to Week 8 in EASI as the dependent variable and treatment group and the randomization stratification variable as factors. The two arms will be compared using a one-sided test at the alpha=0.05 level of significance.		
Secondary efficacy analyses:		
All secondary endpoints defined as the percentage change from Baseline will be analyzed using the same type of ANOVA model as specified for the primary analysis. All change from Baseline		

secondary endpoints will be analyzed using analysis of covariance (ANCOVA) models with treatment group and the randomization stratification variable as factors and with the baseline value of the corresponding endpoint as a covariate. Secondary endpoints that are defined as proportion variables will be analyzed using Pearson's chi-square test or (if more than 25% of expected cell frequencies are less than 5) Fisher's exact test. All secondary analyses will be conducted using one-sided tests at the alpha=0.05 level of significance, with no adjustments for multiplicity.

TABLE OF CONTENTS

PROTO	OCOL AMENDMENT 3.0 SUMMARY OF CHANGES	2
PROTO	OCOL AMENDMENT 2.0 SUMMARY OF CHANGES	3
PROTO	OCOL AMENDMENT 1.0 SUMMARY OF CHANGES	4
SPONS	SOR SIGNATURE PAGE	5
INVES	STIGATOR SIGNATURE PAGE	6
PROCE	EDURES IN CASE OF EMERGENCY	7
SYNOI	PSIS	8
1.	INTRODUCTION	16
1.3.	Study Rationale	21
2.	STUDY OBJECTIVES	
2.1.	Primary Objective	
2.2.	Secondary Objectives	
3.	STUDY ENDPOINTS	23
3.1.	Efficacy Endpoints	23
3.2.	Pharmacokinetic Endpoints	
4.	INVESTIGATIONAL PLAN	
4.1.	Overall Study Design	
4.2.	Study Population and Number of Subjects	
4.3.	Duration of the Study	
5.	STUDY DESIGN SCHEMATIC	25
6.	SCHEDULE OF ASSESSMENTS	
7.	SELECTION OF SUBJECTS	
7.1.	Inclusion Criteria	
7.2.	Exclusion Criteria	

8.	STUDY DRUG	29
8.1.	Description of Study Drug	29
8.2.	Study Drug Packaging and Labelling	29
8.3.	Study Drug Storage	29
8.4.	Randomization and Blinding	29
8.5.	Study Drug Administration and Application	29
8.6.	Study Drug Dispensing and Return	30
8.7.	Study Drug Compliance	30
8.8.	Study Drug Accountability and Disposal	30
9.	CONCOMITANT MEDICATIONS AND PROCEDURES	31
9.1.	Permitted Treatments and Procedures	31
9.2.	Prohibited Treatments and Procedures	31
10.	STUDY PROCEDURES BY VISIT	32
10.1.	Screening Period	32
10.2.	Baseline (Day 1)	32
10.3.	Week 2	33

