4. INVESTIGATIONAL PLAN

4.1. Overall Study Design

The study is a randomized, double-blinded, vehicle controlled, parallel group study, designed to assess the safety, tolerability, and preliminary efficacy of EVO101 Topical Cream, 0.1%, in subjects with mild-to-moderate AD.

Approximately 118 adult subjects, ≥ 18 years of age will be enrolled into this trial. The duration of the study for each subject is expected to be approximately 12 weeks (up to 4 weeks screening, 8 weeks treatment).

Subjects will be in generally good health and have a clinical diagnosis of mild-to-moderate AD for at least one year, an IGA score of 2 or 3, an EASI of 5-20, and an affected BSA of 4-12%. Subjects must be willing to discontinue any therapies for AD and refrain from using any topical or systemic agents for AD, other than the investigational product, during the trial. Subjects will be randomized (1:1), at Baseline, to one of two treatment arms: EVO101 Topical Cream, 0.1%, or vehicle cream. The randomization will be stratified by baseline IGA score (IGA 2, IGA 3). At most 40% of randomized subjects can be in the IGA 2 stratum.

Subjects will be instructed to apply a thin layer of study drug to the affected areas, twice daily, during their trial participation.

Subjects will participate in the trial for 8 weeks in duration and be seen for in-clinic visits at Screening (up to 30 days prior to Baseline), Baseline, Week 2, Week 4 and Week 8 (Study Exit).

Efficacy will be assessed using the IGA for AD (scored from 0-4), EASI, percentage BSA affected, and pruritus (using an 11-point pruritus-NRS; assessing the worst itch in the last 24-hours, by the subject, daily).

Safety will be assessed through physical exam, serum chemistries, hematology, urinalysis, ECGs, AEs, and local skin reactions.

Pharmacokinetic samples will be collected at Baseline, Week 2 and Week 8.

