7.1. Inclusion Criteria

Subjects must meet all of the following criteria to be eligible for study participation:

- 1. Signed informed consent.
- 2. Willing and able to comply with the study visit schedule, procedures, and questionnaires.
- 3. Male or non-pregnant, non-lactating, females, age ≥ 18 years.
- 4. Chronic AD (according to the American Academy of Dermatology Consensus Criteria) that has been present for ≥1 year before the Screening visit.
- 5. Investigator's Global Assessment score of 2 to 3 at Screening and Baseline.
- 6. EASI of 5-20 at screening and baseline.
- 7. BSA of AD involvement, excluding the face and intertriginous areas, of 4% to 12% at Screening and Baseline.
- 8. Application of a stable dose of non-medicated topical moisturizer twice daily for \geq 7 days prior to the Baseline visit and willing to maintain stable dosing during study participation
- 9. Completed electronic diary entries for pruritus for a minimum of 4 of 7 days preceding randomization at the Baseline visit.
- 10. Willing to use effective contraceptive method, if applicable, during study participation and for 30 days following the end of treatment.

For women of childbearing potential: agree to remain abstinent (refrain from heterosexual intercourse) or use a highly effective contraceptive method during the treatment period and for at least 30 days after the last application of study drug.

A woman of childbearing potential is defined as a postmenarcheal female, who has not reached a postmenopausal state (≥ 12 continuous months of amenorrhea with no identified cause other than menopause) and has not undergone surgical sterilization (removal of ovaries and/or uterus).

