10.2. Baseline (Day 1)

- Collect concomitant medication information.
- Measure vital signs.
- Medical history: update medical history if appropriate.
- Perform a physical examination.
- Conduct urine pregnancy test.

- Draw blood sample for pharmacokinetic analysis.
- Collect IGA, BSA and EASI.
- Collect AEs.
- Collect LSRs pre and post study drug application.
- Confirm pruritus-NRS diary data is complete.
- Confirm subject eligibility and enrollment.
- Instruct subject on study medication application and e-diary completion.
- Apply first application in clinic and record in diary.
- Dispense study drug and Subject AD Mapping Image.
- Schedule next visit.

10.3. Week 2

- Collect AEs
- Collect concomitant medication information.
- Measure vital signs.
- Conduct urine pregnancy test.
- Draw blood sample for pharmacokinetic analysis.
- Collect IGA, BSA and EASI.
- Collect LSRs.
- Confirm compliance with pruritus-NRS diary.
- Confirm compliance with study drug application.
- Dispense study drug.
- Schedule next visit.

10.4. Week 4

- Collect AEs
- Collect concomitant medication information.
- Measure vital signs.
- Conduct urine pregnancy test.
- Collect IGA, BSA and EASI.
- Collect LSRs.
- Confirm compliance with pruritus-NRS diary.

- Confirm compliance with study drug application.
- Dispense study drug.
- Schedule next visit.

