15.4.2. Secondary Efficacy Analyses

All secondary endpoints defined as the percentage change from baseline will be analyzed using the same type of ANOVA model as specified for the primary analysis. All change from baseline secondary endpoints will be analyzed using analysis of covariance (ANCOVA) models with treatment group and the randomization stratification variable as factors and with the baseline value of the corresponding endpoint as a covariate. Secondary endpoints that are defined as proportion variables will be analyzed using Pearson's chi-square test or (if more than 25% of expected cell frequencies are less than 5) Fisher's exact test. All secondary analyses will be conducted using one-sided tests at the alpha=0.05 level of significance, with no adjustments for multiplicity.

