8.3.5 Primary Efficacy Analysis

Т

The primary efficacy analysis will be conducted using an analysis of variance (ANOVA) model with the percentage change from Baseline to Week 8 in EASI score as the dependent variable and treatment group and the randomization stratification variable as factors.

Missing data for raw EASI data will be imputed from baseline, and percent change from baseline will then be calculated. The	Change

Protocol title: A RANDOMIZED, VEHICLE-CONTROLLED, SAFETY AND EFFICACY STUDY OF EVO101 IN ADULT SUBJECTS WITH ATOPIC DERMATITIS

Sponsor code: EVO101-AD001

code: EPQ1001

Version number: Final 1.0

Date: 17-AUG-2023

Additionally, a box plot will be created with the percentage of change from baseline as the y-axis and the treatment group as the x-axis.

The primary efficacy analysis will be performed on the ITT population. Derivation of the EASI score is described in appendix 10.1.

A sensitivity analysis of the primary endpoint will be conducted in the PP population.

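### The primary EASI model adjusts for the IGA stratum but not for continuous baseline EASI; adding it is optional, costs under 1% in variance at worst, and gains once |r| exceeds about 0.09

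*Protocol*

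**What the plan says.** Protocol 15.4.1 specifies an ANOVA with "percentage change from Baseline to Week 8 in EASI score as the dependent variable and treatment group and the randomization stratification variable as factors". The Synopsis has the same model. The visible sentence of SAP 8.3.5 says the analysis is "conducted using an analysis of variance (ANOVA) model with the percentage change from Baseline to Week 8 in EASI score" as the response, with the same two factors. Protocol 4.1 and 8.4 identify the stratification variable as baseline IGA with two levels, 2 and 3, and cap the IGA 2 stratum at 40% of those randomized.

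EASI is measured before treatment in everyone. Protocol 10.2 lists "Collect IGA, BSA and EASI", and inclusion criterion 6 requires "EASI of 5-20 at screening and baseline".

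The plan has a stated rule for baseline adjustment. Under Protocol 15.4.2, "All secondary endpoints defined as the percentage change from baseline will be analyzed using the same type of ANOVA model" as the primary, that is, without the baseline value. Endpoints that are absolute changes get an ANCOVA "with the baseline value of the corresponding endpoint as a covariate". SAP 8.6 only points back to 8.3.5 and 8.3.6 for covariates, and parts of both sections are redacted.

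**The concern.** Entry allows a fourfold range of baseline EASI, and a two-level IGA factor can capture only part of it. Dividing by baseline to form a percentage change does not guarantee that the result is uncorrelated with baseline. If a correlation remains within arm and stratum, the planned estimate is less precise than the collected data allow, and a chance imbalance in baseline EASI between arms moves it.

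Only precision is at stake. Under randomization the planned ANOVA has no bias on average and holds its type I error.

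**Working it through.** **Inputs from Protocol 15.8 and 15.4.1:** 59 per arm (N = 118), SD 50 points, difference 30 points, one-sided alpha 0.05.

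**Assumed:** r, the correlation of baseline EASI with percentage change within arm and IGA stratum. The documents do not give it. The range shown is 0 to 0.30, with 0.30 as an upper sensitivity value.

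**1. The plan's own power.** SE of the difference = 50 × √(2/59) = 9.21, so the standardized difference is 30 / 9.21 = 3.26. The normal approximation gives Φ(3.26 − 1.645) = 94.7%. The noncentral t with 115 df (treatment plus stratum) gives 94.46%. The claim of more than 90% is reproduced.

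**2. Effect of adding the covariate.** With two arms, one two-level stratum and one covariate, the expected variance of the treatment effect relative to the ANOVA is

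ratio = (1 − r²) × (1 + 1/(N − 5)) = (1 − r²) × (1 + 1/113).

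The second factor is the price of estimating the slope: 1.0088 at N = 118. The lost degree of freedom moves the critical value only from 1.6582 to 1.6583.

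**3. Break-even.** Setting the ratio to 1 gives r² = 1 − 113/114, so |r| = 0.094. Break-even on power is also 0.094.

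**4. Results.** Power is from the noncentral t with 114 df at 30 points. Equivalent N is 118 / ratio. The half-width is that of a two-sided 90% interval, t × 9.21 × √ratio.

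| r | variance ratio | power | equivalent N | half-width (points) |
|---|---|---|---|---|
| planned ANOVA | 1 | 94.5% | 118 | 15.27 |
| 0 | 1.0088 | 94.3% | 117.0 | 15.33 |
| 0.05 | 1.0063 | 94.3% | 117.3 | 15.31 |
| 0.10 | 0.9988 | 94.5% | 118.1 | 15.26 |
| 0.15 | 0.9862 | 94.7% | 119.7 | 15.16 |
| 0.20 | 0.9685 | 95.0% | 121.8 | 15.02 |
| 0.30 | 0.9181 | 95.9% | 128.5 | 14.63 |

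**5. Simulation check.** Both models were fitted to simulated trials with 40% in the IGA 2 stratum and a linear relation. With 40,000 trials per value of r, the variance ratios were 1.009, 1.001, 0.969 and 0.918 at r = 0, 0.09, 0.20 and 0.30, in agreement with the formula. A separate set of 200,000 trials per value gave a type I error of 4.9% to 5.1% for both models.

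**6. Shift from chance imbalance.** If the arms differ in mean baseline EASI by one standard error, the unadjusted estimate moves by r × 9.21 points: 0.9 at r = 0.10, 1.8 at r = 0.20 and 2.8 at r = 0.30. Adjustment removes this if the relation is roughly linear. It is the same baseline-explained variation already counted in the variance ratio, seen in a single trial; it is not a second gain.

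**7. Smaller analysed N.** The SAP version history limits the multiple-imputation analysis to participants with a baseline and at least one post-baseline assessment, so N may fall below 118. The loss at r = 0 stays under 1% down to N = 106, where it is 1/101 = 0.99%. At N = 100 it is 1/95 = 1.05%, with break-even at |r| = 0.102.

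**The case against.** The case against is that no defect has been shown. The primary follows the plan's own rule for percentage-change endpoints, the test is valid, and the stated power is met. Baseline severity is already partly handled by dividing by baseline, by the IGA factor, and by the EASI and BSA entry limits, so r may well lie near or below break-even. In that case the change gains nothing or loses slightly. The calculation also assumes complete data, a linear relation and constant variance, whereas the plan imputes raw EASI and the endpoint cannot fall below −100%. Finally, redacted parts of SAP 8.3.5, 8.3.6 and 10.2 may already hold a baseline-adjusted analysis. The version history names a multiple-imputation analysis of absolute change in EASI at Week 8, which the Protocol 15.4.2 rule would adjust for baseline.

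Most of this stands, and it is why the change is optional. The sign of the effect depends on an unknown r, and the third and fourth digits of the ratios carry no practical meaning. What survives is the asymmetry: at N = 118 the expected loss is capped near 0.9% of variance, while the gain grows with r². A supportive adjusted analysis behind the redactions would not alter the visible primary model.

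The objection that the change spreads to other endpoints has limited force. No listed secondary endpoint is a percentage change, although SAP 8.3.6 does compare percentage changes in BSA and pruritus.

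**Conclusion.** The point holds as an optional improvement; it does not correct an error. Continuous baseline EASI is collected but absent from the visible primary model. At SD 50 and 59 per arm, adding it changes the variance by +0.9% at r = 0, by nothing at |r| of about 0.09, by −3% at 0.20 and by −8% at 0.30. Power stays between 94.3% and 95.9%, against 94.5% as planned. In subjects, that runs from a loss of about 1 to a gain of about 10.

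This rests on an assumed r, a roughly linear relation and an analysed N near 118. The arithmetic is secure; whether the trial would actually gain is uncertain.

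**What to change.** Before unblinding, prespecify the primary model as percentage change in EASI = treatment + IGA stratum + continuous baseline EASI, and keep the present ANOVA as a supportive analysis. Make the change in the Synopsis, Protocol 15.4.1 and SAP 8.3.5, and align the code in SAP 10.2. Because Protocol 15.4.2 ties other percentage-change endpoints to the primary model, add a sentence saying whether the BSA and pruritus percentage-change comparisons also take their baseline values. If redacted text already contains a baseline-adjusted analysis of percentage change in EASI, the change amounts to swapping the roles of the two analyses.

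The cost is one model term and one degree of freedom, with no new data or subjects. It does need a protocol amendment with ethics approval (Protocol 17.4) and a new SAP version signed before the blind is broken (the route in SAP 8.2). If r is 0, the price is about 0.9% more variance and 0.2 points of power. After unblinding the primary model should not be changed, since a covariate added then could be seen as chosen for its result.

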15.4.2. Secondary Efficacy Analyses

All secondary endpoints defined as the percentage change from baseline will be analyzed using the same type of ANOVA model as specified for the primary analysis. All change from baseline secondary endpoints will be analyzed using analysis of covariance (ANCOVA) models with treatment group and the randomization stratification variable as factors and with the baseline value of the corresponding endpoint as a covariate. Secondary endpoints that are defined as proportion variables will be analyzed using Pearson's chi-square test or (if more than 25% of expected cell frequencies are less than 5) Fisher's exact test. All secondary analyses will be conducted using one-sided tests at the alpha=0.05 level of significance, with no adjustments for multiplicity.

15.5. Adverse Events

All AEs that occur during the study will be recorded and classified on the basis of Medical Dictionary for Regulatory Activities (MedDRA) terminology. TEAEs are defined as AEs with an onset on or after the date of the first study drug application. AEs noted prior to the first study drug administration that worsen after baseline will also be reported as AEs and included in the summaries.

All information pertaining to an AE noted during the study will be listed by subject, detailing the verbatim term given by the Investigator or designee, preferred term, system organ class, onset date, resolution date, severity, seriousness, action taken, outcome and drug relatedness. The event onset will also be shown relative (in number of days) to date of first application.

Treatment-emergent AEs will be summarized by treatment group, the number of subjects reporting a TEAE, system organ class, preferred term, severity, relationship to study drug (causality) and seriousness. When summarizing AEs by severity and relationship, each subject will be counted once within a system organ class or a preferred term by using the event with the highest severity and greatest relationship within each classification.

Serious AEs will be summarized by treatment group, severity and relationship to study drug, and individual SAEs will be listed by subject. In addition, a list of subjects who prematurely discontinue from the study due to an AE will be provided.

15.5.1. Local Skin Reactions

Local Skin Reaction assessments (LSRs) include burning/stinging, pruritus, edema/swelling, erythema, dryness, and scaling. LSRs will be scored as 0 (None), 1 (Mild), 2 (Moderate) or 3 (Severe).

LSRs will be summarized by visit using descriptive statistics. A by-subject listing of subjects with any LSR scored as 3 will be presented.

15.6. Other Safety Data

Laboratory test results will be summarized descriptively at baseline and Week 8. Additionally, shifts from baseline to Week 8 in laboratory test results based on normal ranges will be summarized with descriptive statistics. Individual laboratory test results will be presented in a by-subject listing. Any clinically significant laboratory abnormalities will be captured as AEs.

Vital signs will be presented by treatment group as observed values and changes from baseline using descriptive statistics.

Medical histories will be coded using the MedDRA dictionary and presented in a by-subject listing.

Concomitant medications will be coded using the WHO-Drug dictionary. Concomitant medications will be summarized by treatment, drug class and preferred term.

Physical examination data will be presented in a by-subject listing.

Descriptive statistics by treatment group and visit will be provided for the following ECG parameters: heart rate (HR), RR duration, QRS duration, PR duration, QT duration and QTcF and QTcB duration.

15.7. Pharmacokinetic Analysis

Plasma concentration data will be tabulated and summarized (geometric mean, arithmetic mean, minimum, maximum, SD, and % coefficient of variation) by treatment group for each visit at which samples were taken.

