10.5. Week 8 (Study Exit/Early Withdrawal)

- Perform physical exam.
- Collect AEs.
- Collect concomitant medication information.
- Measure vital signs.
- Collect ECG.
- Draw blood samples for laboratory tests and urine for urinalysis and urine pregnancy test.
- Draw blood sample for pharmacokinetic analysis.
- Collect IGA, BSA and EASI.
- Collect LSRs.
- Confirm compliance with pruritus-NRS diary.
- Confirm compliance with study drug application.
- Close e-diary and exit subject from study.

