14.3. Study Drug Discontinuation

Subjects who discontinue or have their study drug discontinued prematurely should continue to have all protocol-specified safety assessments and end of study procedures collected.

The Investigator should stop study drug treatment in the following instances:

- Inter-current illness that would, in the judgment of the Investigator, affect assessments of clinical status to a significant degree.
- Any AE which is clinically significant, is deemed persistent, is probably or definitely related to study drug in the judgment of the Investigator.
- Unacceptable toxicity.

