15.2. Populations Analyzed

All subjects who are randomized will be included in the intent-to-treat (ITT) population.

Per-protocol (PP) population: All subjects in the ITT population who complete the Week 8 evaluation without any significant protocol violations

PK population: All subjects who had blood collected for PK analysis will be included in the PK population.

All subjects who are randomized and receive at least one confirmed dose of study drug will be included in the safety population.

The primary efficacy analysis and the analysis of all secondary endpoints will be performed using the ITT population Additional supportive efficacy analyses will be performed using the PP population. In all efficacy analysis, subjects will be included in the treatment arm to which they were randomized. Safety analyses will be performed using the safety population. In all safety analyses, subjects will be analyzed based on the treatment that was received.

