The study is a randomized, double-blinded, vehicle controlled, parallel group study, designed to assess the safety, tolerability, and preliminary efficacy of EVO101 Topical Cream, 0.1%, in subjects with mild-to-moderate AD.

Approximately 118 adult subjects, ≥18 years of age will be enrolled into this trial. The duration of the study for each subject is expected to be approximately 12 weeks (up to 4 weeks screening, 8 weeks treatment) attending to the following visits: Screening (up to 30 days prior to Baseline), Baseline, Week 2, Week and Week 8 (Study Exit).

Subjects will be in generally good health and have a clinical diagnosis of mild-to-moderate AD for at least one year, an IGA score of 2 or 3, an EASI of 5-20, and an affected BSA of 4-12%. Subjects must be willing to discontinue any therapies for AD and refrain from using any topical or systemic agents for AD, other than the investigational product, during the trial.

Protocol title: A RANDOMIZED, VEHICLE-CONTROLLED, SAFETY AND EFFICACY STUDY OF EVO101 IN ADULT SUBJECTS WITH ATOPIC DERMATITIS

Sponsor code: EVO101-AD001

code: EPQ1001

Version number: Final 1.0

Date: 17-AUG-2023

6 Determination of Sample Size

7 Data Sets to be Analyzed

The following analysis sets will be used for the statistical analysis and presentation of data:

- The Intent-to-treat (ITT) population will consist of all randomized subjects.
- The Per-Protocol (PP) population will consist of the subset of the ITT population who
 - complete the Week 8 evaluation and have evaluable data for the EASI and IGA assessments at Week 8.
 - have no significant protocol deviations through the Week 8 visit.
- The Pharmacokinetic (PK) population will consist of all ITT subjects who have a pre-dose and at least one post-dose blood sample collected for plasma drug concentration analysis.
- The Safety (SAF) population will consist of all subjects who receive at least one confirmed dose of study drug.

The final criteria for the PP population, regarding the protocol deviations that warrant exclusion, will be determined during the pre-analysis review when all data on protocol deviations are available and before breaking the blind.

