- Day 1 through Day 7 values will be based on the single assessments performed on each subject on that day.
- Baseline, Week 1, Week 2, Week 3, Week 4, Week 5, Week 6, Week 7 and Week 8 values will be based on the average pruritus-NRS score of the 7 days prior to the visit date. Subjects with less than 4 values in the 7 days prior to the visit date will have that visit value considered missing.
- Summary statistics at baseline, Day 1, Day 2, Day 3, Day 4, Day 5, Day 6, Day 7, Week 1, Week 2, Week 3, Week 4, Week 5, Week 6, Week 7 and Week 8 will be provided by each treatment group as well as the change and percentage of change from baseline.
- Comparison between treatments in the change and percentage change from baseline to each visit will be conducted in the ITT and PP populations.
- Number and percentage of subjects achieving a 4-point improvement in the pruritus-NRS score from Baseline to Week 8 in subjects who had an average maximum pruritus-NRS score of at least 4 at Baseline. Comparisons between treatments will be made in the ITT and PP populations.
- A listing with the visit, date of the assessment, score, change and percentage from baseline and the flags of 4-point improvement achievement.

Pharmacokinetics:

Plasma levels of EVO101 will be evaluated by:

- Summary statistics at baseline, Week 2, and Week 8 will be provided for the active treatment group.
- A listing with the visit, date of the assessment and value.

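### The Week 8 PK summary has no visible on-drug condition, so samples from subjects who have stopped study drug can lower the reported exposure

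*Protocol*

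**What the plan says.** The secondary objective (Protocol 2.2) is the pharmacokinetics of the cream when applied twice daily. The endpoint (Protocol 3.2) is the plasma level at Baseline, Week 2 and Week 8.

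- **Who is sampled.** Protocol 14.3: "Subjects who discontinue or have their study drug discontinued prematurely should continue to have all protocol-specified safety assessments and end of study procedures collected". The visit in Protocol 10.5 serves as Week 8, study exit and early withdrawal, and its list of procedures includes "Draw blood sample for pharmacokinetic analysis".
- **Who is in the PK population.** Protocol 15.2: "All subjects who had blood collected for PK analysis will be included in the PK population". SAP 7 is narrower: "all ITT subjects who have a pre-dose and at least one post-dose blood sample collected for plasma drug concentration analysis".
- **What is summarised.** Protocol 15.7 tabulates concentrations "by treatment group for each visit at which samples were taken", with geometric and arithmetic mean, minimum, maximum, SD and %CV. SAP 8.3.6: "Summary statistics at baseline, Week 2, and Week 8 will be provided for the active treatment group". The output is Table 14.2.3.1, and Listing 16.2.6.5 gives the individual values.

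No visible text makes inclusion depend on continued application or on time since the last application.

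**The concern.** A summary meant to describe systemic exposure under twice-daily use should rest on samples from subjects who were using the cream. The rules as written also admit a sample from a subject who had stopped. Under SAP 7 that sample still counts as post-dose, however long ago the last application was. If the subject attends at Week 8, the sample is correctly labelled Week 8, so better visit assignment would not remove it.

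At stake is the descriptive estimate of systemic exposure to a topical drug. Where levels have fallen after stopping, the means move in one direction only, towards lower exposure. The grounds for stopping in Protocol 14.3 include drug-related adverse events and unacceptable toxicity, so the subjects who have stopped need not be a random subset.

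**Working it through.** The documents state no PK figure, so there is none to reproduce. The check has two parts.

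**1. Can an off-drug sample reach the Week 8 summary?** Protocol 14.3 retains the subject for end-of-study procedures. Protocol 10.5 draws PK blood at that visit. Protocol 15.2 admits anyone with a sample, and SAP 7 admits anyone with a pre-dose and a post-dose sample. Protocol 15.7 and SAP 8.3.6 then summarise by visit. No step removes the sample. A subject who leaves early has the same draw at the same combined visit. The SAP 10.1 time window for early withdrawals covers efficacy assessments only, so the documents do not say whether that PK sample counts as Week 8.

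**2. What would it do to the summary?** Inputs:

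- Planned active arm: 59 (Protocol 15.8).
- f, the share of active-arm Week 8 samples taken off drug: **assumed**, 5% to 20%. With 59 subjects this is about 3 (0.05 × 59 = 2.95), 6 (5.9) or 12 (11.8).
- r, the off-drug level as a fraction of the on-drug level: **assumed**, 0.5 down to 0.01. The documents give no discontinuation rate, half-life or quantification limit.

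Pooled mean divided by on-drug mean:

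- arithmetic: 1 − f(1 − r)
- geometric: r^f

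| f | Arithmetic, r = 0.5 | r = 0.1 | r = 0.01 | Geometric, r = 0.5 | r = 0.1 | r = 0.01 |
|---|---|---|---|---|---|---|
| 5% | 0.975 | 0.955 | 0.951 | 0.966 | 0.891 | 0.794 |
| 10% | 0.950 | 0.910 | 0.901 | 0.933 | 0.794 | 0.631 |
| 20% | 0.900 | 0.820 | 0.802 | 0.871 | 0.631 | 0.398 |

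At f = 0 or r = 1 both ratios are 1. At r = 0 the arithmetic ratio is 1 − f, and the geometric mean is undefined without a rule for values below the quantification limit. No such rule is visible. As an illustration only, suppose such values are set to half the limit and the on-drug geometric mean is 5 to 20 times the limit. Then r = 1/(2 × 5) = 0.1 to 1/(2 × 20) = 0.025, and the geometric mean falls by 11–17%, 21–31% and 37–52% at f = 5%, 10% and 20%.

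**Spread and extremes**, for off-drug values near zero, with on-drug mean m, SD s and CV = s/m:

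- Pooled variance = (1 − f)s² + f(1 − f)m². This exceeds s² only if CV² < 1 − f, that is, if the on-drug CV is below √(1 − f): 97%, 95% and 89% at f = 5%, 10% and 20%. Above that, the SD falls.
- Pooled CV² = (CV² + f)/(1 − f), which is always larger than CV². The %CV therefore rises.
- Adding lower values cannot reduce the maximum. It can reduce the minimum.

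**The case against.** The strongest reply is that the affected group may be small or empty. Protocol 14.3 does not say that subjects who stop drug stay until Day 56. Several reasons for stopping are also grounds for leaving the study (Protocol 14.2), and a subject who withdraws consent is to be seen as soon as possible. Subjects long off drug who still attend at Week 8 are therefore only a subset of those who stop, and f = 20% has no support in the documents. This stands, and it limits what can be said about size. It does not supply the missing condition.

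Second, there are safeguards. Week 2 gives another summary that is less exposed to the problem. Listing 16.2.6.5 shows dates and can be cross-referenced to the exposure listing (16.2.5.1). The blinded review in SAP 8.2 can document how specific data issues are handled. These help a reader trace an off-drug value, but the main table stays as it is unless someone decides otherwise. The PK listing as described in SAP 8.3.6 does not show time since last application.

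Third, parts of SAP 8.1, 8.3.6 and 8.3.7 are not visible, and the PK manual (Protocol 13.4) is not among the documents, so a rule there cannot be excluded. That is why the point is limited to visible text. Both population definitions, Protocol 15.7 and the PK items in SAP 8.3.6 are readable and contain no such rule.

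Fourth, a strict diary filter could drop subjects who were on drug but made no entry. SAP 8.3.7 itself anticipates incorrect ePRO exposure data. This stands, and the fix allows for it.

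A reader might go further and infer that exposure **is** understated, that the SD is necessarily inflated, or that the highest observed level is hidden. The documents do not support these readings. The first needs subjects who stopped, enough washout and measurable on-drug levels. The second holds only below the CV threshold shown above. The third is wrong, because the maximum is not lowered.

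**Conclusion.** The point holds in conditional form. Followed as written, the readable PK rules put any off-drug end-of-study sample labelled Week 8 into a summary meant to describe twice-daily use. If such samples exist and levels have fallen, the arithmetic mean drops by f(1 − r): 2.5% to 5% at f = 5%, and 10% to 20% at f = 20%, as r goes from 0.5 to 0. The geometric mean drops by more, by an amount that depends on an unstated rule for values below the quantification limit. Both f and r are assumptions, and with f = 0 there is no effect.

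The geometric figures matter only if the list of statistics in Protocol 15.7 is followed. The visible general rule for continuous data in SAP 8.3.2 gives mean, SD, median and range, and the median is less sensitive to a few low values. This is a descriptive analysis in a phase 2a trial and no hypothesis test depends on it. It is a cheap improvement worth making before unblinding.

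**What to change.** In SAP 7 and 8.3.6, and in Protocol 15.7:

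1. Base the main Week 8 PK summary in Table 14.2.3.1 on samples taken while the subject was on study drug, and apply the same rule at Week 2 for consistency. Define on-drug status from the last application date already used for exposure in SAP 8.3.7, and state before unblinding the longest gap between application and sample that still counts.
2. Resolve missing or incorrect diary entries with drug accountability and the blinded pre-analysis review, rather than excluding a sample automatically because an entry is absent.
3. Show the all-samples summary alongside as supportive.
4. Add an off-drug flag and days since last application to Listing 16.2.6.5.

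While these sections are open, reconcile the two PK population definitions and state how values below the quantification limit enter the geometric mean.

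The cost is a short SAP text and one derived flag, with no new data collection. The main summary may lose a few samples and depends to some degree on diary quality. Tube counts alone will not date a last application. The on-drug summary describes subjects who were still applying the cream, which is a further reason to keep the all-samples version beside it.
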